### 535 **Affective Well-Being Measures**

536 **1. Depression Episodes** will be operationalized in a manner consistent with other studies in  
537 perimenopausal depression and based on the following assessments: **The Center for**  
538 **Epidemiologic Studies Depression scale (CES-D)** is a 20-item self-report form assessing  
539 depressed mood. CES-D scores  $\geq$  16 have been consistently validated as defining high  
540 depressive symptoms suggestive of clinically significant DEP (positive predictive value=75%),  
541 and this cut-point has been used to define depressive episodes in multiple perimenopausal  
542 samples. Moreover, elevated CES-D scores have been shown to be sensitive to the anti-  
543 depressant actions of ERT in PM women. **Thus, CES-D scores  $\geq$  16 will be used to**  
544 **operationally define ‘depression episodes’.** However, if CES-D scores are  $>$  10 at any study  
545 visit then the Structured Clinical Interview for DSM-IV (non-patient edition) will be

546 administered to determine the presence of either minor or major depression. **Functional**  
547 **Impairment:** We will use the widely used Medical Outcomes Study 36-item short form (SF-  
548 36), which yields scores of general health perceptions, physical functioning, role limitations due  
549 to physical functioning, social functioning, bodily pain, general mental health, role limitations  
550 due to emotional problems, and vitality. The rationale for the selection of this instrument is  
551 based on: 1) the demonstration that it is sensitive to change over time; 2) its incorporation of  
552 subscales to specifically assess functional impairment related to emotional and physical  
553 symptoms as well as overall social functioning; 3) its able to discriminate subgroups of CVD  
554 patients known to have poorer survival and worse disease; and 4) normative data for this scale  
555 are available for the general US population as well as 13 medical conditions. **Symptom**  
556 **Severity and Affective Instability** will be assessed with the CES-D scale (at baseline and  
557 months 2,4,6,8,10 and 12), the former with a repeated measures approach and the latter by the  
558 variance in the CES-D score over 12 months.

559 **Lifetime Trauma Exposure** will be assessed by a validated interview. A cumulative (total)  
560 trauma score will be generated by assigning one-point for each of the following 15 traumas: **1)**  

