684 as long as the time required in the present study. Risks of dizziness associated with  
685 nitroglycerine will naturally be minimized since subjects will be in the supine position and  
686 instructed to stand up slowly. While headache may develop, our prior experience with this  
687 procedure is that headaches were mild, short-lived, and did not interfere with function.

688

689 Psychological risks associated with the interviews and stress testing are minimized via the use of  
690 clinically trained interviewers and highly competent and professional staff. Frequent contact  
691 with subjects and frequent assessment of depressive symptoms (months 1, 2, 4, 8, 10, and 12)  
692 will minimize the risk that a worsening of depressive symptoms would go undetected. Risks  
693 associated with phlebotomy will be minimized by using sterile materials, by applying pressure to  
694 the skin upon removal of the needle, and by placing each subject in the reclined position to  
695 minimize risk of syncope. Risks of loss of confidentiality will be minimized by the use of  
696 subject codes linked to all data and by maintaining the file linking the subject code to the name  
697 in a separate secure location. All databases will be stored on a secure, HIPAA compliant  
698 network. The server is backed up nightly. The database is also protected by logins and  
699 passwords required to open the system. Different levels of privileges are granted to different  
700 users. This study will use a web-based, secure, password protected access to the database.  
701 Passwords will be changed every 90 days.

702

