755 that it is medically necessary to become unblinded to treatment assignment, he will be able to do  
756 so very quickly.

757 We also have a plan for the monitoring of medical conditions that may emerge during the course  
758 of the 12 month study requiring treatment or withdrawal. The development of hypertension or  
759 hyperlipidemia represent the most likely medical conditions that may emerge over a 12 month  
760 interval in perimenopausal women. Our protocol allows for the frequent monitoring of BP levels  
761 (months 1, 2, 4, 6, 8, 10, and 12) throughout the protocol. Consistent with JNC 7 guidelines, the  
762 detection of BP levels during the study in the Stage 1 HTN range (140 – 159 mmHg SBP or 90 –  
763 99 mmHg DBP) will prompt monthly reassessments of BP to confirm BP status, and a review of  
764 the American Heart Association (AHA) dietary and physical activity guidelines with the subject.  
765 If the average BP over any 3 consecutive months remains in the Stage 1 HTN range, the subject  
766 will be withdrawn and referred for treatment. Detection of BP levels consistent with Stage 2  
767 HTN at any point will prompt immediate withdrawal and referral. Fasting LDL cholesterol will  
768 be measured at months 6 and 12 (Time 1 and 2 testing). However, in women with LDL-  
769 cholesterol > 190 mg/dl at month 6, a level for which the NCEP recommends therapeutic  
770 lifestyle changes and LDL-lowering drugs, we will re-assess fasting lipid profiles at months 8  
771 and 10. Should LDL again exceed 190 mg/dl on either determination, the subject will be  
772 withdrawn from the study and referred for treatment. If a subject develops coronary heart  
773 disease, venous thromboembolism, breast or endometrial or ovarian cancer, or biliary tract  
774 disease, she will be withdrawn from the study. Our plan to enroll only medically healthy  
775 perimenopausal women and to educate, encourage, and assess compliance with the AHA diet  
776 and exercise guidelines will minimize the development of medical conditions requiring  
777 withdrawal.

778 **General Statistical Considerations:** This is a two between subjects and one within-subjects  
779 (repeated measure) design. The two between-subjects factors are treatment (ERT or placebo,  
780 randomized) and history of DEP (positive or negative, non-randomized), and the within-subjects  
781 factor is time (psychiatric outcomes at months 0 (baseline), 1, 2, 4, 6, 8, 10, and 12, and CV  

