880 analyses of baseline data as two-group analyses rather than a main effect in a two-by-two  
881 factorial. The Stress Reactivity composite score as the response. If the null hypothesis is  
882 rejected, we will examine the same contrast for metabolic risk (as a parallel logistic regression  
883 model since it is categorical), flow mediated dilatation, and baroreceptor sensitivity.

884 **Aim 1 Hypothesis 2:** This secondary analysis will add the effect of trauma to the model, and  
885 assess whether trauma moderates the effect of DEP history on CV risk variables (above).

886 **Aim 2 Hypothesis 1:** In the mixed random coefficients model we will use for this repeated  
887 measures analysis, we will test this hypothesis using a contrast that examines the difference  
888 between the women with and without histories of DEP on the difference between the month 0  
889 and month 12 least squares means. This contrast will be done in the context of the full model but  
890 involves means from 2 of the 4 between-subjects cells. If this null hypothesis is rejected, we will  
891 test the same hypotheses for flow mediated dilatation and baoreceptor sensitivity (mixed model),  
892 and examine metabolic risk (categorical) via parallel logistic regression model.

893 **Aim 2 Hypothesis 2:** We will fit a two-factor logistic regression predicting the presence or  
894 absence of DEP episodes during the follow-up period. If we reject the null hypothesis, we will  
895 follow this with a two-factor mixed random coefficient model using CED-D, functional  
896 impairment and (using without the repeated measures portion since affective instability is  
897 defined over the entire follow-up period) affective instability as defined earlier. Further, as  
898 sensitivity analyses, we will examine the same effect on number of episodes / month during the  
899 follow-up period, using Poisson regression, and on the CES-D scores themselves using a mixed  
900 model.

901 **Aim 3 Hypothesis 1 (A and B):** With stress reactivity as the response, we will test these  
902 hypotheses in the context of the two between-factor one-repeated factor mixed random  
903 coefficient model we listed earlier. Hypothesis H1A is the main effect for treatment, predicting  
904 that the difference between the change in LSMs from month 0 to month 12 will be in different  
905 directions in the treated and untreated women. If this null hypothesis is rejected, we will examine  

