906 parallel effects on metabolic risk (via a logistic regression), baroreceptor sensitivity, and flow  
907 mediated dilatation. Hypothesis H1B involves partitioning the interaction effect in these models.

908 **Aim 3 Hypothesis 2:** This will be examined in a logistic regression model with two between-  
909 subjects factors (DEP history and treatment) and the emergence of at least one DEP episode as  
910 the response. This is the treatment main effect in the model. If we reject the null hypothesis, we  
911 will examine the same hypothesis using CED-D total (mixed model), functional impairment  
912 (mixed model), number of episodes (Poisson regression), and affective instability (mixed model).

913 **Aim 3 Hypothesis 3 (secondary):** This hypothesis will use a logistic regression model with two  
914 between-subjects factors as above, the emergence of at least one DEP episode as the response,  
915 and stress reactivity in the model as a mediator.

916

917 **POWER AND SAMPLE SIZE CALCULATIONS FOR EACH SPECIFIC AIM:**

918 It is not feasible to conduct power analyses for every hypothesis. While this is a mechanistic  
 919 study designed, in part, to examine mediators of E2's beneficial effects on CV risk and DEP, we  
 920 must first be able to detect a beneficial effect of E2. Thus, we conduct power for Aim 3, H2.  
 921 We also felt it important, however, to confirm we are powered to detect meaningful differences  
 922 in the Stress Reactivity composite score since it is our primary CV outcome variable and also a  
 923 predicted mediator.

924 **Aim 3 Hypothesis 2:** Based on the work of Freeman et al (Menopause, 2009. **16**(4): p. 728-34)  
 925 for rates in untreated women, and our prediction that ERT will cut the rate of depression by 50%  
 926 (a clinically relevant difference), we predict the following percentages of women will experience  
 927 at least one DEP episode during the follow-up in our groups:

928

		Treatment Assigned	
		ERT	Placebo
Depression	Positive	22.5	45
History	Negative	15	30
(Combined)		(18.75%)	(37.5%)

929

930 The hypothesis corresponds to using logistic regression to test the depressive episode rate  
 931 between all those treated with ERT (18.75%) versus those treated with placebo (37.5%). Using a  
 932 logistic regression with this effect size, a two-tailed significance level of 0.05, and 240 total  
 933 subjects, power exceeds 96%. Further, power should be higher for the parallel poisson  

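### Aim 3 H2 models a raw count of depressive episodes with no exposure term, although Aim 2 H2 models the same outcome per month and women can leave early (minor)

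*Protocol*

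**What the plan says.** **Episode.** Under Affective Well-Being Measures, a CES-D score of 16 or more is used to "operationally define ‘depression episodes". An episode can therefore be seen only where a CES-D is completed.

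**Aim 2 H2** (Data Analytic Plan). After the logistic regression: "sensitivity analyses, we will examine the same effect on number of episodes / month during the" follow-up period, by Poisson regression. The outcome is a rate.

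**Aim 3 H2** (same section). The follow-on list, run only if the logistic null is rejected, includes "mixed model), number of episodes (Poisson regression), and affective instability (mixed model". No denominator is given. The Power and Sample Size section again describes the Poisson analysis as one of the number of episodes, and expects it to have more power than the logistic test.

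**Early exit.** Monitoring and Reporting of Adverse Events gives withdrawal rules for blood pressure, LDL and several diagnoses. For sustained Stage 1 readings the subject "will be withdrawn and referred for treatment. Detection of BP levels consistent with Stage 2" hypertension leads to immediate withdrawal.

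**CES-D schedule.** It is given in three ways:
- General Statistical Considerations: "factor is time (psychiatric outcomes at months 0 (baseline), 1, 2, 4, 6, 8, 10, and 12, and CV" measures at months 0, 6 and 12.
- Affective Well-Being Measures: baseline and "months 2,4,6,8,10 and 12), the former with a repeated measures approach and the latter by the" variance of the score.
- Protection Against Risk: "with subjects and frequent assessment of depressive symptoms (months 1, 2, 4, 8, 10, and 12", without month 6.

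**The concern.** Aim 2 and Aim 3 give the same outcome two different definitions, and only one allows for unequal follow-up. In the Aim 3 model a woman who leaves at month 2 with no episode counts the same as one who completes 12 months with none. Each early exit lowers the expected count in her arm, whatever her mood.

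The treatment comparison is randomized, but time under observation is not protected by randomization. The protocol lists increased blood pressure among the less frequent estradiol side effects, and withdraws women for raised blood pressure, so unequal exit is plausible. It could run either way: more exits on ERT would flatter treatment, and more exits on placebo would hide a benefit.

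**Working it through.** **Inputs.** From the protocol: the post-baseline visits under each of the three schedules, and 12 months of treatment. Assumed: the share d of each arm that leaves, all leaving just after the month 2 visit, and no true effect. The protocol states no dropout rate and no figure for either Poisson analysis, so there is no published figure to reproduce.

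**Formulas.** Let V be the visits of a completer and v those of a woman leaving at month 2. If the chance of a positive score is the same at every visit:
- expected count per woman is proportional to C(d) = (1−d)·V + d·v
- expected months per woman is M(d) = (1−d)·12 + d·2
- raw-count ratio = C(d2)/C(d1), as Aim 3 is written
- ratio with a months offset = [C(d2)/M(d2)] / [C(d1)/M(d1)]

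Here d2 is the arm with more dropout.

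**Schedule 1, 2, 4, 6, 8, 10, 12 (V = 7, v = 2).**
- 15% v 35%: C = 0.85·7 + 0.15·2 = 6.25 and 0.65·7 + 0.35·2 = 5.25. Raw ratio 5.25/6.25 = **0.84**. M = 10.5 and 8.5. Months offset: (5.25/8.5)/(6.25/10.5) = 1.04.
- 10% v 40%: C = 6.5 and 5.0. Raw ratio 5.0/6.5 = **0.77**. M = 11.0 and 8.0. Months offset: (5.0/8.0)/(6.5/11.0) = 1.06.
- Equal dropout: both ratios are 1.00.

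**All three schedules, same formulas.**

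| CES-D visits (months) | V, v | Raw, 15% v 35% | Raw, 10% v 40% | Months offset, same two cases |
|---|---|---|---|---|
| 1, 2, 4, 6, 8, 10, 12 | 7, 2 | 5.25/6.25 = 0.84 | 5.0/6.5 = 0.77 | 1.04, 1.06 |
| 2, 4, 6, 8, 10, 12 | 6, 1 | 4.25/5.25 = 0.81 | 4.0/5.5 = 0.73 | 1.00, 1.00 |
| 1, 2, 4, 8, 10, 12 | 6, 2 | 4.6/5.4 = 0.85 | 4.4/5.6 = 0.79 | 1.05, 1.08 |

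The raw count is biased on every schedule. The months offset removes most or all of that bias.

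**Does the counting rule matter?** Women enter non-depressed, so a constant chance per visit is a simplification. A two-state model was run on the first schedule (assumed onset 0.05 per month, mean episode length 0.25 to 4 months, 10% v 40% leaving at month 2). It counted either every positive visit or each unbroken run of positive visits as one episode.
- Raw count: 0.72 to 0.77 under both rules and all lengths.
- Months offset: 0.99 to 1.06.
- Offset of completed assessments: 0.93 to 1.00.

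The raw-count bias keeps its direction and rough size throughout.

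**The case against.** **The offset may simply be unstated.** The Aim 3 entry is one item in a list, and an offset is often left to a statistical analysis plan, which is not shown. That is fair, and the Aim 3 wording may be shorthand. But the protocol does specify the outcome in both places, once per month and once as a number, so the two texts need to agree.

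**The analysis carries little weight.** This largely stands. Aim 2's model is labelled a sensitivity analysis. Aim 3's is gated on the logistic test, and episode count does not appear in the hierarchy set out under the H2 hypothesis itself. The power remark has no figure attached.

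**Differential dropout is assumed.** It is. Some withdrawals would also come late: LDL withdrawal follows re-testing at months 8 and 10, when less follow-up is lost.

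**A stronger reading to avoid.** A reader might infer that months are the wrong denominator too. On the first schedule a completer has 7/12 = 0.58 assessments per month and a woman leaving at month 2 has 2/2 = 1.00. That suggests a rate 1.71 times too high for her (1.14 for exit at month 6), and an offset of completed assessments as the remedy. The documents do not support this:
- On the even schedule under Affective Well-Being Measures, assessments per month are 0.50 at every exit visit and the excess is nil.
- The direction depends on a counting rule that the protocol does not give. In the two-state model with 4-month episodes and every positive visit counted, a woman leaving at month 2 has a per-month rate of about 0.85 times a completer's.
- With positive visits counted and episodes of 2 or 4 months, the group ratio (10% v 40%) is 1.01 or 0.99 with months, against 0.95 or 0.93 with assessments. The months offset is then the less biased.

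What survives concerns missed visits: a completer who misses one of seven has 6/7 = 0.86 of the usual chances to record a positive score.

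**Conclusion.** The Aim 3 H2 Poisson analysis, as written, lacks the exposure term that Aim 2 H2 has for the same outcome. With no true effect and exits at month 2, the count ratio is about 0.84 for 15% v 35% leaving and about 0.77 for 10% v 40%. For the latter it is 0.73 to 0.79 across the three schedules with a constant chance per visit. These sizes rest on assumed dropout, and equal follow-up gives no bias. The claim that Aim 2's per-month rate is itself materially wrong is not established, and the choice between months and assessments there is open. Because both Poisson analyses are supportive, the point is minor and does not touch the primary logistic test.

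**What to change.** 1. In Aim 3 H2, fit the Poisson model with log follow-up time as offset, the same exposure as in Aim 2 H2, and describe the outcome as a rate in both places and in the power section.
2. In both aims, limit counts and exposure to scheduled visits in months 1 to 12. Otherwise extra mood reassessments after deterioration, and the optional CES-D calls at months 15 to 24, could enter the count.
3. Reconcile the three CES-D schedules.
4. State whether consecutive scores of 16 or more are one episode or several.
5. Optionally, add an offset of log completed CES-D assessments as a sensitivity analysis for missed visits, not as a replacement for months.

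The cost is a few lines of text and no new data, since visit dates and completed CES-D forms are already part of the record. An offset corrects for time observed. It does not correct for exit that is itself caused by worsening mood.

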 934 regression on number of episodes, and for the analysis of the CES-D scores themselves.

935 **Aim 1, H1:** Our primary hypothesis for Aim 1 involves Stress Reactivity and since we cannot  
 936 assert that any stress-responsive factor is more important than another in this context, we will  
 937 combine different measures of stress-responsive CV risk factors and combine them into an index  
 938 called Stress Reactivity, described above. Since this measure has not been used before, we do  
 939 not have information from prior research on means and standard deviations which could help  
 940 with power and sample size calculations. Instead, we performed power calculations for each of  
 941 the stress reactivity variables which comprise the composite score. We used differences between  
 942 DEP and non-DEP groups from Pace et al. (Am J Psychiatry, 2006. **163**(9): p. 1630-3) for IL-6;  
 943 from Young et al. (Neuropsychopharmacology, 2000. **23**(4): p. 411-8) for cortisol; from  
 944 Brownley et al. (Am J Obstet Gynecol, 2004. **190**(4): p. 1052-8) for clinically relevant  
 945 differences in MAP; and from [name] (Health Psychol, 2007. **26**(2): p. 201-13; Int J  
 946 Psychophysiol, 1994. **17**(3): p. 233-48).for group differences in VRI – using the reported group  
 947 differences to define the magnitude of differences which are important, and to obtain estimates  
 948 of SDs. We obtained effect sizes of 0.63, 0.86, 1.0, and 1.5 for differences in delta MAP, VRI,  
 949 IL-6, and Cortisol, respectively. Our sample size of 160 per DEP group yields **99% power to**  
 950 **reject a null hypothesis** of no effect for an effect size of 0.63, (the smallest above), and 80%  
 951 power to detect an effect size as small as 0.40. Due to the complexity of the random coefficient

952 model to be used for this variable, we approximated our calculations with a simpler ANOVA  
953 power on change scores. Our actual power should be higher because the model should be more  
954 precise.

955 **Inducements for Participation**

956 Total possible monetary inducement for participating = \$1,275, prorated as follows:

957 \$100 for the medical and psychiatric screening (these screenings also provide benefit in the form  
958 of free medical evaluations)

959 \$150 for each laboratory test session (\$450 total)

960 \$100 for each flow mediated dilatation procedure (\$300 total)

961 \$ 25 for each interim study visit (\$125 total)

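### Episode counts go into Poisson regression with no rule for when consecutive high CES-D scores are one episode, and the claim of higher power has no calculation behind it

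*Protocol*

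**What the plan says.** All references are to the protocol.

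- *Affective Well-Being Measures* defines a depression episode as a CES-D score of 16 or more. It gives no duration, gap or remission rule.
- *Data Analytic Plan*, Aim 3 Hypothesis 2: if the logistic test of at least one episode rejects, further outcomes follow, among them "number of episodes (Poisson regression").
- *Data Analytic Plan*, Aim 2 Hypothesis 2 uses a rate instead: as "sensitivity analyses, we will examine the same effect on number of episodes / month during the" follow-up period, again by Poisson regression.
- *Power and Sample Size Calculations*, Aim 3 Hypothesis 2, states more than 96% power for the logistic test with 240 women. It continues: "Further, power should be higher for the parallel poisson" "regression on number of episodes, and for the analysis of the CES-D scores themselves". No mean count, dispersion or calculation is given.
- *Multiple Testing* allows the other variables to be examined only after the primary null hypothesis is rejected.

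**The concern.** CES-D is scored repeatedly over 12 months. On the literal definition, a woman who scores high at months 4, 6, 8 and 10 has four episodes, although she may have had one illness. Counts of that kind cluster within women, so their variance exceeds their mean. A Poisson model with model-based errors assumes that the two are equal. Its intervals would be too narrow, and its apparent gain in power over the binary test would partly reflect invalid errors.

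The opposite problem arises if runs are merged. Few women can then have more than one or two episodes, the variance falls below the mean, and model-based errors are too large. The protocol does not say which case applies, yet it asserts a power advantage. The two aims also describe the outcome differently: a monthly rate in Aim 2, and a count with no exposure term mentioned in Aim 3.

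**Working it through.** **Inputs from the protocol.** The predicted proportions with at least one episode are 22.5% and 15% on ERT and 45% and 30% on placebo (history positive and negative), combined 18.75% and 37.5%. The test is two-sided at 0.05 with 240 women, 120 per arm. *General Statistical Considerations* gives seven post-baseline psychiatric visits (months 1, 2, 4, 6, 8, 10, 12). *Affective Well-Being Measures* omits month 1 for CES-D; seven are used here.

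**Assumed, not in the protocol.** The tendency of a high score to persist within a woman, shown as a range.

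**Step 1: the stated benchmark.** Two-proportion test, mean proportion 0.28125:

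- Pooled SE = √(2 × 0.28125 × 0.71875 / 120) = 0.0580
- Unpooled SE = √((0.1875 × 0.8125 + 0.375 × 0.625) / 120) = 0.0568
- Power = Φ((0.1875 − 1.96 × 0.0580) / 0.0568) = 90.3%

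Other forms at 240 give 88.9% (logit Wald) to 91.0% (unpooled). The same formula with 160 per arm gives 96.5%. So the stated figure matches 320 women rather than 240. That is a separate point, but it sets the benchmark: about 90 to 92% at 240.

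**Step 2: each high visit counted, by formula.** With seven visits, mean probability p of a high score and within-woman correlation ρ, variance/mean = (1 − p)(1 + 6ρ). Here p is set so that 28.1% of women have at least one high score. The SE is too small by the square root of this ratio D, and the type I error is 2(1 − Φ(1.96/√D)). For ρ = 0.2, p is about 0.073, so D = 0.927 × 2.2 = 2.04, √D = 1.43, and the error is 2(1 − Φ(1.37)) = 17%. Power is simulated at 60 women per cell.

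| ρ (assumed) | Variance/mean | SE factor | Type I error, plain | Power, robust | Power, logistic |
|---|---|---|---|---|---|
| 0.1 | 1.50 | 1.23 | 11% | 90% | 92% |
| 0.2 | 2.04 | 1.43 | 17% | 85% | 91% |
| 0.3 | 2.55 | 1.60 | 22% | 84% | 91% |
| 0.4 | 3.05 | 1.75 | 26% | 83% | 90% |

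Plain Poisson shows 95 to 96% power in these runs.

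**Step 3: each high visit counted, by a second model.** A two-state Markov chain with visit-to-visit persistence s was simulated, with 240 women, the protocol's cell rates and 1,500 trials per scenario. Under the null, both arms have the placebo rates.

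| s (assumed) | SE factor (null) | Type I error, plain | Power, robust | Power, logistic |
|---|---|---|---|---|
| 0.3 | 1.15 | 10.5% | 85.9% | 90.3% |
| 0.5 | 1.35 | 15.6% | 82.4% | 90.9% |
| 0.7 | 1.57 | 22.9% | 79.1% | 90.3% |
| 0.85 | 1.73 | 27.2% | 83.1% | 91.1% |

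With 320 women the order is the same: robust Poisson 88.7 to 94.2%, logistic 96.1 to 96.7%.

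**Step 4: runs collapsed to one episode, same chain, 240 women.** Dispersion is 0.70 to 0.87. Plain Poisson type I error is 1.9 to 3.2%. Power is 87.5 to 90.6% plain and 91.7 to 93.6% robust, against about 90 to 91% for logistic.

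**Step 5: independent visits.** Dispersion is about 0.95, and plain Poisson power is 94.5% against 91.0% for logistic. Among the visit-count scenarios, only this one gives the promised gain with valid errors.

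**The case against.** A reader might infer that the protocol counts every high score as a separate event, so that the standard errors are certainly too small and false positives several times nominal. The text does not support that. It never says how repeats are counted, and where it describes past depression it treats an episode as a continuous illness (a single past episode lasting at least three months, for example). On that reading plain Poisson can err in the conservative direction.

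Four further points carry weight:

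- **The gate.** The error rates above belong to the Poisson test alone. In Aim 3 it is run only after the logistic test rejects. With no treatment effect, a false Poisson claim cannot then occur more often than that gate opens, nominally 5%.
- **Depression history is a factor in the Aim 3 model.** The average difference between the two history groups is therefore already accounted for. Persistence within a woman is not.
- **A statistical analysis plan may exist.** It could specify a robust variance or an offset, and the protocol does promise to check distributional assumptions. The absence of those details is not itself the finding.
- **The size rests on assumed persistence.** The protocol gives no value for it.

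These points limit the importance of the problem. They do not supply a counting rule, and they do not support the power sentence, which is a positive statement in the protocol rather than a detail left for later.

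**Conclusion.** The point holds in conditional form. The episode count is undefined where scores repeat, and plain Poisson errors can be wrong in either direction depending on how that is settled:

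- **Visit counts:** errors too small by about 1.15 to 1.75, and the test's own type I error about 10 to 27% before the gate.
- **Collapsed runs:** type I error about 2 to 3% under Markov persistence.

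The ranges rest on assumed correlation of 0.1 to 0.4 or persistence of 0.3 to 0.85, and on seven visits.

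The claim of higher power is unsupported. It would be too strong to say that the count analysis always has less power than the binary test. With valid errors at 240 women, power is usually lower for visit counts (about 79 to 90% against 90 to 92%). It is about equal, if anything slightly higher, for collapsed counts, and higher if visits are independent. The protocol states none of these conditions.

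The consequence is limited to a gated secondary analysis in Aim 3 and a sensitivity analysis in Aim 2. The primary logistic test does not depend on it.

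**What to change.** 1. State that a run of consecutive CES-D scores of 16 or more counts as one episode.
2. In both aims, use Poisson regression with a robust (sandwich) variance. It is valid under over- or underdispersion. A negative binomial model would handle only overdispersion and so would not suit collapsed counts.
3. In both aims, include log follow-up time or log number of CES-D assessments as an offset.
4. Delete the statement of higher Poisson power, or replace it with a calculation that states the counting rule, mean count and dispersion.

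These are changes of wording and analysis only, with no new data, visits or participants. The only downside is that intervals may become wider.
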